### **Sample size**

A total sample size of a minimum of 40 patients was established for this study. This number is based on

$$n = \frac{2 \cdot (Z_\alpha + Z_\beta)^2 \cdot \sigma^2}{d^2}$$

where:

$Z_\alpha = 1.96$ , based on a confidence of  $P=0.05$  (false rejecting of a true null hypothesis),  
 $Z_\beta = 0.84$ , based on a power of 80% (failure to reject a false null hypothesis),  
 $d = 1.0$  inch reduction in waist circumference as a meaningful/successful change in measurement,  
 $\sigma = 1.50$  inches, based on the evidence presented by a published study under similar treatment parameters and conditions reporting a typical response of 0.75 inches through the umbilical region and assuming some of the population may not respond at all.

The resulting calculation gives a population size of 37. Accounting for possible attrition and adding a generous margin of safety, a recruitment size of 50 individuals is arrived at. Review of the data analysis shall be conducted by an independent entity to confirm the handling and calculation of data, and the conclusions drawn from the data regarding statistical significance.

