**Efficacy of Low-Frequency, High-Intensity Ultrasound  
for Reduction in Subdermal Adipose Layers**

Device Investigated: Ultimate Contour Body Sculpting Device

Indication Studied: Application of ultrasound for non-invasive waist circumference reduction.

A randomized, blinded comparison of waist circumference reduction of an active test group vs. a placebo control in adults.

Sponsor: CAO Group, Inc.

Protocol ID: 005-00036-8

Development Phase: Performance Validation

NCT ID: Not Yet Assigned

Anticipated Initiation Date: 15 December 2019

Anticipated Completion Date: 1 May 2020

Document Date: 10 October 2019

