## **Recruitment**

Recruiting shall consist of about 50 patients, with a target of at least 40 patients completing the study. Should patients drop out of the protocol such that 37 patients are not achieved at the end of the study, additional patients shall be recruited to achieve the target number.

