### Patient population

The population for this study shall consist of adults age 18 and over. Recruiting efforts shall focus on obtaining a reasonably even number of male and female patients and to include patients exhibiting a body mass index (BMI) of 25 or higher. No concern or focus will be given regarding the ethnicity of the patients, although a wide range of ethnicities would be beneficial. Patients will be evaluated relative to the inclusion and exclusion criteria indicated below. A recruitment target of a total of 50 patients is established. During recruitment, each candidate will be assigned a test subject number for identification purposes.

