#### **RECRUITMENT/SCREENING (total time of activity, 2-3 weeks):**

- Advertisement shall be made in social media channels regarding the study. This method is thought to be appropriate to bring the study to the attention to prospective participants located in the vicinity close to the study site.
- An appointment is made with a prospective patient, where the candidate is evaluated according to the inclusion and exclusion criteria, and medical history and medications. The purpose and protocol of this study are discussed, any candidate questions or concerns are addressed, and the consent form is presented. The candidate may sign the consent form at this time, or arrange for time to further review their participation. Women participating in the study who are of child-bearing age or capable of becoming pregnant shall take a pregnancy test. Patient Information, Medical History, and Medication forms are presented for the patient to populate.

- Recruitment continues until 50 included candidates are identified and consent obtained on those candidates.
- A candidate is accepted to participate after the following are confirmed by the principal investigator:
  - The Informed Consent Form is signed
  - The Patient Information Form is completed and the patient is not excluded due to any of the indicated criteria
  - The Medical History and Medication forms are populated and reviewed to ensure the candidate does not meet any of the exclusion criteria or other circumstances that may put the candidate at elevated risk by participating.

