### **Statistical methods planned, including handling data exclusion, analysis of sub-groups if any**

Any patient that did not conclude all three treatments shall be excluded from the analysis. If there are fewer than 37 patients remaining after the study concludes and exclusions are applied, than no analysis shall take place and additional study subject enrolled until a minimum of 40 completed participants exist. In the event that a patient concludes at least one treatment session, but afterwards discontinues

participation in the study, the presence of the patient in the study shall be acknowledged for data analysis purposes. Missing data for such acknowledged participants shall be fulfilled by inserting the least favorable result obtained realized from among all test subjects who did complete the study. Statistical analysis shall then proceed on the fully populated study data.

Primary analysis shall consist of applying the Anova single-factor acceptance test evaluating the change in waist circumference based on the data collected by the tape measure. A confidence of  $P=0.05$  shall be applied. The results of this data shall be directly applied to determining if the primary objective of the study has been met.

A correlation analysis shall be applied to all variable data recorded, as well as key calculations from the data, to identify any potential two-way connections or relationships between sets of data. Any correlations scoring a magnitude of 0.85 or greater shall be discussed and if appropriate, Anova single-factor analysis applied to determine if there is statistical significance to the relationship and any statements that might be supported by the data. Of primary interest is any impact the starting BMI might have on the amount of change, and any impact that gender may impart to the outcome.

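### The sample-size formula gives a number per group, but its result is used as the whole-study total; as a two-arm trial, 40 completers give about 54% power, not 80%

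*Combined protocol and SAP*

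**What the plan says.** The Sample size section prints n = 2(Zα + Zβ)²σ²/d², with Zα = 1.96, Zβ = 0.84, d = 1.0 inch and σ = 1.50 inches. It attributes σ to a published study "reporting a typical response of 0.75 inches through the umbilical region", with an allowance for people who do not respond. It then states "The resulting calculation gives a population size of 37".

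That figure is carried through the plan as a count of all patients:

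- Sample size: "A total sample size of a minimum of 40 patients was established for this study".
- Synopsis, Recruitment: further patients are recruited "Should patients drop out of the protocol such that 37 patients are not achieved at the end of the study".
- Statistical methods planned: analysis is withheld and enrolment reopened "If there are fewer than 37 patients remaining after the study concludes and exclusions are applied".
- Patient population: "A recruitment target of a total of 50 patients is established".
- Recruitment/Screening: "Recruitment continues until 50 included candidates are identified".

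No per-group number and no allocation ratio appears anywhere.

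The plan disagrees with itself on the design. The title page describes "A randomized, blinded comparison of waist circumference reduction of an active test group vs. a placebo control in adults". The Synopsis (Statistical Methods) tests the test group against the control group by single-factor ANOVA. The secondary objective mentions a Test group, and Sequence and duration of study period mentions the group to which a patient is assigned. Study configuration says instead that the study has one arm and that every eligible candidate is treated with the device.

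**The concern.** The factor of 2 comes from the variance of a difference between two independent means, so the formula answers how many patients are needed in each of two groups. Reading the answer as the size of the whole study halves a two-arm trial. The stated 80% power would then not be a property of the trial: a true 1-inch difference would be missed nearly half the time, and a null result could be misread as evidence that the device does not work.

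The number also operates as a rule. The 37-patient floor decides whether the analysis goes ahead, so in a two-arm trial it would permit the primary test at roughly coin-flip power.

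If the study has one arm, the formula does not fit the design, though the error then makes the study larger than it needs to be. Until the design text is reconciled, a reader cannot tell which case applies.

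**Working it through.** **Inputs from the Sample size section:** Zα = 1.96 (two-sided 5%), Zβ = 0.84 (80% power), d = 1.0 inch, σ = 1.50 inches.

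**Assumptions, not stated in the plan:** σ is the standard deviation (SD) of the change in waist circumference, and two-arm allocation is 1:1.

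**1. The plan's own figure.** 2 × (1.96 + 0.84)² × 1.5² / 1.0² = 2 × 7.84 × 2.25 = 35.28, so 36 per group. With the noncentral t distribution, 36 per group gives 79.7% power and 37 per group gives 80.8%. The plan's 37 therefore matches the t-test number per group. The two-arm total is 72 (normal approximation) to 74 (t-test).

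**2. Power if the plan's numbers are two-arm totals.** Two-sided 5% t-test, which for two groups is the same as single-factor ANOVA. The noncentrality is d / (σ√(1/n₁ + 1/n₂)); for 20 + 20 this is 1.0 / (1.5 × √0.1) = 2.11.

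| Completers | Split | Power for 1.0 inch | Difference detectable at 80% |
|---|---|---|---|
| 37 (floor) | 18 + 19 | 50.4% | 1.42 inches |
| 40 (target) | 20 + 20 | 53.8% | 1.36 inches |
| 50 (all recruited) | 25 + 25 | 63.7% | 1.21 inches |

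Unequal allocation lowers power: 27 + 13 gives 48.6%.

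**3. If the study has one arm, tested against zero change.** Without the factor of 2: 7.84 × 2.25 = 17.64, so 18. By the t-test, 20 patients are needed (80.7%). Power is 97.6% with 37 patients and 98.4% with 40.

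**4. If σ is the SD of a single measurement.** The SD of the change is then 1.5 × √(2(1 − r)), where r is the correlation between baseline and week 12. The plan gives no r, so a range is shown for 20 + 20:

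| r (assumed) | SD of change | Power, 20 + 20 |
|---|---|---|
| 0 | 2.12 | 31% |
| 0.5 | 1.50 | 54% |
| 0.73 | 1.10 | 80% |
| 0.8 | 0.95 | 90% |

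The 18 + 19 floor reaches 80% at about r = 0.75. On this reading one arm of 37 has 79.7% power at r = 0 and 97.6% at r = 0.5.

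**The case against.** The strongest reply is that the operative text points to one arm. Study configuration is the section dedicated to design. The treatment procedure describes one setting for everyone, recruitment has no randomization step, and no sham procedure is given. On that reading there is no shortfall. This stands as a condition: the 54% applies only to a two-arm trial. It does not rescue the derivation, because a two-sample formula does not size a one-arm study.

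A second reply is that 37 can be a correct total. If single-factor ANOVA compares baseline with week 12 in one arm, and σ is the SD of a single measurement, the formula counts patients per occasion, and 37 give about 80%. This needs zero correlation between two waist measurements on the same person, which the plan does not state. The Sample size section also ties σ to a typical response and to non-responders, which suggests variation in the change.

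A third point is fair and affects the rewording. The primary objective asks for statistical significance and also for a reduction of at least 1 inch. If the true mean change is exactly 1.0 inch, an observed mean reaches 1 inch only about half the time at any sample size. Reading the rule as a condition on the mean, simulation gives about 50% for both conditions together with one arm of 40. With 20 + 20 and no change in controls it gives about 39%. The powers in the working are for the significance test alone.

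**Conclusion.** The concern holds. The formula gives 36 per group (37 by the t-test), and the plan uses that per-group figure as a total. If the trial is the randomized comparison, power for a 1.0-inch difference is 53.8% with 40 completers, 50.4% at the floor and 63.7% if all 50 complete. These figures rest on an SD of change of 1.5 inches and 1:1 allocation; the mismatch between per-group and total does not depend on either. If the study has one arm, power is not short (97.6% with 37), but the formula and the link from 37 to 80% are still wrong with σ as the SD of change. If σ is a single-measurement SD, two-arm power depends on a correlation that the plan does not supply. The point must be fixed, because the stated power and the 37-patient rule both rest on this calculation.

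**What to change.** 1. **Settle the design.** Reconcile Study configuration with the title page, the Synopsis (Statistical Methods), the secondary objective and Sequence and duration of study period.
2. **If two-arm,** state the allocation ratio and replace the sentence reporting 37 with, for example: *The formula gives 36 patients per group (37 by the t-test), 72 to 74 in total. With 40 completers in two equal groups, power of the significance test is about 54% for a 1.0-inch difference in change, and 80% for about 1.36 inches.* Stop presenting 37 or 40 in total as securing 80% power in the Synopsis (Recruitment), Statistical methods planned and Sample size.
3. **If single-arm,** use (Zα + Zβ)²σ²/d² = 17.64, so 18 (20 by the t-test), and state that 37 completers give about 98% power against zero change.
4. **In either case,** say that σ is the SD of the change (or give r), label 1.50 an assumption if its derivation is not shown, and say that the power refers to the significance test and not to the joint 1-inch success rule.

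**Cost.** Correcting the sample-size statement is a matter of wording and needs no extra patients, but a two-arm plan would then state a less favourable power. Settling the design also touches the sections listed in step 1, and a two-arm plan would need its allocation and control arrangements written down. Actually reaching 80% for 1.0 inch with two arms would need 72 to 74 completers. At the plan's ratio of 50 recruited to 40 completing, that is 72/0.8 = 90 to 74/0.8 = 92.5, so 90 to 93 recruited. That ratio includes a safety margin as well as attrition, so the recruitment figure is only a guide.
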